**ISSUE**

**Effects of Polarized and Threshold Intensity Distribution Models on Running Time and  
Body Composition in Recreational Runners Aged 20 to 45 Years: A Randomized  
Controlled Trial**

## **Primary Objective**

To compare the effects of polarized and threshold TID models over 12 weeks on 5 km running time in recreational runners aged 20-45 years.

## **Secondary Objective**

To compare the effects of polarized and threshold TID models over 12 weeks on body composition in recreational runners aged 20-45 years.

## **Specific Objectives**

- Characterize the sample of recreational runners between 20 and 45 years old by the initial assessment of 5 km running time and body composition before the intervention.
- Apply polarized and threshold intensity distribution models (IDM) as intervention strategies in the assigned groups for 12 weeks.
- Evaluate the changes in 5 km running time and body composition between the groups subjected to the polarized DIE model and the threshold TID model after 12 weeks of intervention.

## **Study Assumptions**

### **Primary Alternative Hypothesis**

The polarized TID model is superior by at least 60 seconds in 5k running time, compared to the threshold TID in a 12-week program in recreational distance runners.

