### **Primary Null Hypothesis**

No differences in 5k running time were identified between the polarized TID model compared to the threshold TID model in a 12-week program in recreational distance runners.

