### **Sample Size Calculation**

The sample size was calculated using EPIDAT version 4.2 for independent samples, considering a 95% confidence level ( $\alpha = 0.05$ ) and 80% statistical power ( $\beta = 0.20$ ). A standard deviation of 60 seconds was used, taken from previous studies of 5 km races in a similar population (Cruz et al., 2022), and a minimum clinically relevant difference of 60 seconds in race time between the groups was established. Under these assumptions, an approximate sample size of 8 participants per group was estimated; however, to strengthen the validity of the study and anticipate possible losses during follow-up, it was decided to include 10 participants per group, for a total of 20 participants.

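### The primary alternative claims a benefit of at least 60 seconds, but the null and the sample size address only a difference from zero, so rejecting the null cannot support that claim

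*Protocol*

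**What the plan says.** Three places in the protocol bear on this.

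- Primary Alternative Hypothesis: "The polarized TID model is superior by at least 60 seconds in 5k running time", compared with the threshold model over 12 weeks. This is directional and carries a 60 s threshold.
- Primary Null Hypothesis: "No differences in 5k running time were identified between the polarized TID model compared to the threshold TID model". This is a null of zero, with no margin.
- Sample Size Calculation: a "minimum clinically relevant difference of 60 seconds in race time between the groups" with an SD of 60 s, alpha 0.05 and "80% statistical power" for independent samples. Here 60 s is the effect to be detected, and no superiority margin enters.

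Two further sections give context. The Primary Objective is only to compare the two models on 5 km time. The Secondary Alternative Hypothesis says the polarized model is superior in body composition, with no minimum amount.

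**The concern.** The same 60 s does two different jobs: a threshold to be exceeded in the alternative, and a planning difference in the sample size. The null against which the data would be judged is zero. The two primary hypotheses are therefore not complementary. A true polarized advantage above zero but below 60 s, or any advantage for the threshold model, falls under neither.

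The practical risk lies in the primary conclusion. A reader who sees the null rejected, and sees only one alternative written down, could conclude that polarized training saves at least 60 s over 5 km. The data might at the same time be compatible with almost no benefit.

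**Working it through.** **Inputs.** From Sample Size Calculation: SD 60 s, planning difference 60 s, alpha 0.05, power 80%, 8 per group calculated and 10 per group planned. Assumptions: the test is two-sided (the section gives a 95% confidence level but no sidedness); all 10 per group complete (losses are anticipated but no rate is given); and SD 60 s applies to the analysed quantity. The SD is taken from 5 km race studies, while Specific Objectives speaks of changes, whose SD may differ. The difference is threshold minus polarized time, so positive values favour polarized.

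**The plan's own figure.** n per group = 2 × (1.96 + 0.84)² × 60² / 60² = 2 × 7.85 = 15.7, so 16 (17 with the t distribution). One-sided 0.05 gives 13 (14 with t). The stated 8 is not reproduced; it equals 7.85 rounded up, which is the formula without its factor of 2. That is a separate point. What matters here is that the calculation sets 60 s against zero and contains no margin.

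**What rejecting the stated null shows.**
- SE = 60 × √(2/10) = 26.8 s.
- Smallest significant difference = t(0.975, 18 df) × SE = 2.101 × 26.83 = 56.4 s.
- 95% CI at that point = 56.4 ± 56.4, or about 0 to 113 s.

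The null can thus be rejected by an estimate that is itself below 60 s.

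**What showing more than 60 s would need.** The lower 95% limit exceeds 60 s only if the observed difference is above 60 + 56.4 = 116.4 s. The probability comes from a noncentral t with 18 df and noncentrality (true difference − 60)/26.83:

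| True difference | Noncentrality | Two-sided 0.05 | One-sided 0.05 |
|---|---|---|---|
| 60 s | 0 | 2.5% | 5% |
| 90 s | 1.12 | 18% | 28% |
| 120 s | 2.24 | 56% | 69% |

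At two-sided 0.05, 80% is reached at a true difference of about 139.5 s. The 60 s row is true by definition: at the boundary of a margin the probability equals the one-sided alpha, whatever the sample size or SD.

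**Sensitivity.**
- With 8 completers per group, SE = 60 × √(2/8) = 30 s. The critical difference is 64.3 s (CI 0 to about 129 s), and the lower limit passes 60 s only above 60 + 64.3 = 124.3 s. The chances at 90 s and 120 s fall to 15% and 46%.
- With 10 per group the critical difference is 2.101 × √0.2 = 0.94 times the SD. For illustration, an assumed SD of 40 s gives 37.6 s and 80 s gives 75.2 s.

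In every case the interval at the point of significance starts at zero, so the logical gap does not depend on these inputs.

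**The case against.** The strongest reply is that 60 s was never meant as a margin. The sample size section calls it the minimum clinically relevant difference, and writing the design effect into the research hypothesis is a common, if loose, habit. That is probably what happened, and it makes this a wording defect rather than an invalid test. It does not remove the defect: the alternative as written makes 60 s part of the claim, and no other section says otherwise. Nor is this detail that a protocol normally leaves to the analysis plan, because the conflicting statements both stand in the protocol.

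A reader might infer three stronger things that the protocol does not support.

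- *That the trial has only 2.5% power for its own claim.* That figure belongs to a margin test the protocol never states, holds for any trial at the boundary of its margin, and is 5% at one-sided 0.05. It is not a measured weakness of this design.
- *That a significant result will be reported as proving at least 60 s.* The protocol gives no reporting or decision rule to that effect. It is a risk, not a documented plan.
- *That a smaller benefit, or one favouring the threshold model, could lead to no valid conclusion.* The objective is neutral and the null is zero, so a two-sided test supports a conclusion in either direction and at any size. Only the phrase about at least 60 s would be unsupported.

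**Conclusion.** The point holds as a mismatch between the primary alternative on one side and the primary null and sample size on the other. Rejecting the stated null cannot establish the stated alternative. Under two-sided 0.05, SD 60 s and 10 completers per group, significance begins at an observed 56 s, whereas an interval wholly beyond 60 s needs more than 116 s. True differences well above 60 s would often fail to produce such an interval. The exact figures move with sidedness, losses and the SD of the analysed quantity; the conclusion does not. Severity: should-fix. The wording is wrong and governs the primary conclusion, but the zero null itself is testable and the repair is small.

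**What to change.** Reword the Primary Alternative Hypothesis along these lines: 5 km running time differs between the polarized and threshold models in a 12-week programme (two-sided, alpha 0.05). Two-sided wording matches the null and the neutral objective. Leave the outcome definition as planned; this change should not settle whether final time or change is analysed.

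Add that 60 s is the planning difference and the relevance benchmark against which the estimate and its 95% CI are read. Add also that rejecting the null does not by itself establish a benefit of at least 60 s, and that such a claim would need the whole 95% CI to lie beyond 60 s.

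The cost is a few sentences, to be settled before the data analysis shown in Table 12, and a weaker headline claim. If a claim of more than 60 s is truly intended, the null must become a polarized advantage of 60 s or less, and the sample size must assume a larger true effect. By the normal approximation at 80% power and two-sided 0.05, that is 2 × 7.85 × 60²/30² = 62.8, so 63 per group, for a true 90 s, and 2 × 7.85 × 60²/60² = 15.7, so 16 per group, for a true 120 s.

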### **Secondary Alternative Hypothesis**

The polarized TID model is superior in body composition compared to the threshold TID model in a 12-week program in recreational distance runners.

### **Primary Null Hypothesis**

No differences in 5k running time were identified between the polarized TID model compared to the threshold TID model in a 12-week program in recreational distance runners.

### **Secondary Null Hypothesis**

No differences in body composition were identified between the polarized TID model compared to the threshold TID model in a 12-week program in recreational long-distance runners.

## Methodology

### Variables

Two variables were considered: dependent and independent. The dependent variables included running time, measured as total time in minutes/seconds, and body composition, measured as body fat percentage, muscle mass percentage, and body mass index (BMI kg/m^2). These variables were affected by the independent variables, which were the polarized and threshold DIE models (see Table 1). As Gil Pascual (2015) argues, there was one dependent categorical variable, with as many categories as there were groups, and a set of discriminant independent variables, in which the different groups were assumed to differ.

### Operationalization of Variables

**Table 3.** Operationalization of the variables.

Variable	Nature	According to its continuity	Values or unit of measurement	Function in the study	Verification method
Age	Quantitative (For reason)	Continue	Years	Independent or confounding variable (depending on the design)	Citizenship card
Gender	Qualitative Nominal	Discrete (nominal)	Male / Female	Confusing or controlling	Citizenship card
5K race time	Quantitative That makes sense	Continue	Minutes and seconds (e.g., 25:45)	Dependent	5K Test
Body composition	Quantitative That makes sense	Continue	% body fat, % muscle mass, body mass index (BMI kg/m  )	Dependent or confusing	Bioimpedance scale
Muscle mass	Quantitative That makes sense	Continue	Kilograms or percentage (%)	Dependent	Bioimpedance scale

Source: own elaboration.

## **Research Approach**

Regarding the research approach, the research idea, objectives, and variables to be investigated are considered. The approach adapted to this project is quantitative. As Gil Pascual (2015) states, the quantitative approach in the research process, in most cases, aims to generalize results to a target population using data from a sample randomly drawn or selected from that population. In this process, statistical hypotheses about population parameters are formulated based on knowledge of the sample. The researcher must distinguish between research hypotheses, formulated as conjectures about a topic of scientific interest, and statistical hypotheses, formulated in statistical terms of probability about one or more population parameters. Examples of these hypotheses can be found in educational research when decisions are being made about the effectiveness of one teaching method compared to another, or when assessing whether certain relationships between variables observed in a sample also exist in the population. These are just two examples, among countless others, where hypothesis testing must be performed.

## **Type of Research**

Two-arm parallel randomized controlled clinical trial (RCT) designed with the CERT and CONSORT guidelines, Friedman, Furberg, DeMets, Reboussin and Granger (2015).

Furthermore, in relation to the research approach and in accordance with the objectives and variables to be investigated, the design type is experimental, as stated by Ñaupas Paitán et al. (2018). Experimental design allows for establishing the consequences achieved after applying an experiment. In this method, the researcher controls the independent variable, which is generally a treatment, applies it to the dependent variable, and explains what has happened.

Experiments manipulate treatments, stimuli, influences, or interventions (called independent variables) to observe their effects on other variables (dependent variables) in a controlled situation. In other words, experimental designs are used when the researcher intends to establish the possible effect of a manipulated cause.

In this research, the aim is to determine the effects of polarized, and threshold DIE intensity distribution models on running time in recreational runners between 20 and 45 years old.

## **Scope of the Investigation**

In accordance with the complexity of the research objectives, its scope is explanatory, as supported by Ñaupas Paitán et al., 2018. Explanatory studies are based on properly formulated problems that seek to establish cause-and-effect relationships. They necessarily work with hypotheses that explain the effect of independent variables on the dependent variable. This is a more complex, deeper, and more rigorous level of basic research, whose main objective is the verification of causal or explanatory hypotheses; the discovery of new socio-scientific laws, of new social micro-theories that explain the causal relationships of the properties or dimensions of facts, events within the system, and social processes. They work with causal hypotheses, meaning they explain the causes of facts, phenomena, events, and natural or social processes. At this level

of research, the formulation of hypotheses is fundamental because they guide the research path. Investigating without hypotheses is like walking in the jungle or sailing on an ocean without a compass, as we will see later when analyzing the importance of hypotheses.

## Inclusion and Exclusion Criteria

**Table 4.** *Inclusion and exclusion criteria*

Inclusion	Exclusion

 
• Age between 20 and 45 years
 
• 1 to 3 years of experience
 
• Men's race time between 25:00 and 40:00
 
• Women's race times between 28:00 and 43:00
 
• Residing in Bogotá or surrounding municipalities at an altitude of 2,640 meters above sea level
 
• Have a GPS system
 
	
 
• Having a chronic non-communicable disease
 
• Smokers or drinkers
 
• Having some musculoskeletal injury.
 
• DO NOT sign the informed consent form
 
• 10% compliance with training sessions.
 

Source: own elaboration.

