**c. Assignment**

The assignment of participants to each of the groups was in the order in which the initial assessments were carried out.

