## **Information Biases**

For the pre and post-tests and the monitoring of training, an open trial will be conducted where the researchers and coaches will know the groups assigned (POL group and THR group) to each of the participants.

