1. TID POL
2. TID THR

## **TID POL and THR models**

Regarding the intervention, it will last 12 weeks, a period during which physiological adaptations to resistance training occur, as Neuman (1994) states with chronological cycles of 8 to 12 weeks. Now, we will go into detail about how the interventions will work with the DIE models. For the TID POL model, the intensity distribution was as follows: Zone 1 (80%), Zone 2 (5%), and Zone 3 (15%). For the TID THR model, the intensity distribution was as follows: Zone 1 (50%), Zone 2 (40%), and Zone 3 (10%), in the three-zone model according to Skinner and McLellan (1980). This will be monitored using the theoretical heart rate model developed by Tanaka, Monahan, and Seals (2001). The training periodization for the two TID models was designed using a 3:1 weekly block structure, meaning three weeks of training followed by one week of recovery. The weekly training frequency will consist of four running sessions, each including 10 minutes of running technique drills and two strength training sessions. The running sessions will have the same training volume across the three blocks, which span weeks 1-3, 5-7, and 9-11. The first week of each block will have a volume of 240 minutes, the second week 300 minutes, and the third week 360 minutes. Recovery weeks 4, 8, and 12 will have a volume of 180 minutes. Strength training sessions will be held on Mondays and Fridays, with a weekly volume of 60 minutes. Rest days from the running component will be Monday, Friday, and Sunday. The general structure of the intervention is shown in Table 7 below.

**Table 7.** *General structure of interventions with TID models*

Training component	Load component	Weeks of intervention											
		1	2	3	4	5	6	7	8	9	10	11	12
Career	Volume (Minutes/Week)	240	300	360	180	240	300	360	180	240	300	360	180
	Training frequency (Sessions/Week)	4	4	4	4	4	4	4	4	4	4	4	4
Force	Volume (Minutes/Week)	60	60	60	60	60	60	60	60	60	60	60	60
	Training frequency (Sessions/Week)	2	2	2	2	2	2	2	2	2	2	2	2
Running technique	Volume (Minutes/Week)	40	40	40	40	40	40	40	40	40	40	40	40
	Training frequency (Sessions/Week)	4	4	4	4	4	4	4	4	4	4	4	4

Source: own elaboration

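### Table 4 lists training compliance, with no usable threshold, as an exclusion; it can be known only after assignment, so applying it would exclude randomised runners and can bias the comparison

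*Protocol*

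**What the plan says.** Protocol, Inclusion and Exclusion Criteria, Table 4: the last entry but none in the exclusion column is "10% compliance with training sessions". It stands beside chronic disease, smoking or drinking, musculoskeletal injury and lack of signed consent. No other section explains it.

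Other sections fix its context:

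- **Design** (Type of Research): "Two-arm parallel randomized controlled clinical trial (RCT) designed with the CERT and CONSORT guidelines".
- **Assignment** (section c, Assignment): "The assignment of participants to each of the groups was in the order in which the initial assessments were carried out".
- **Training** (TID POL and THR models): "Regarding the intervention, it will last 12 weeks", and "The weekly training frequency will consist of four running sessions, each including 10 minutes of running technique drills and two strength training sessions". Table 7 gives four running and two strength sessions in each of the 12 weeks. No training period before assignment is described.
- **Blinding** (Information Biases): "an open trial will be conducted where the researchers and coaches will know the groups assigned". Programming and Monitoring puts the training programme and its monitoring in the hands of the project's researchers.
- **Numbers** (Sample Size Calculation): 8 per group, raised to 10 partly to "anticipate possible losses during follow-up". No loss rate is given, and compliance exclusions are not mentioned.

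**The concern.** An eligibility criterion has to be decidable before randomisation. Compliance with the trial's own sessions does not exist until the runner has been assigned and has trained. Used as an exclusion, it takes randomised runners out of the trial because of how they responded to their programme. Those left in each arm are then the runners who kept to that arm's programme, and randomisation no longer guarantees that the two sets are comparable.

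Two features add to the risk. The line does not say whether it concerns attendance below, at or above 10%, or absence above 10%; which sessions are counted; or when. And the people who would have to interpret it know each runner's arm. With 10 runners per arm, a few such decisions could matter.

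**Working it through.** **1. When compliance can be known.** Assignment is tied to the initial assessments. All sessions in the protocol belong to the 12-week programme that follows. Without a run-in, any compliance figure is a post-assignment figure.

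**2. What the threshold could be.** Runs: 4 x 12 = 48. Strength sessions: 2 x 12 = 24. Total: 72.

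| Reading | Of 48 runs | Of 72 sessions |
|---|---|---|
| Excluded at or below 10% attended | 0.10 x 48 = 4.8 | 0.10 x 72 = 7.2 |
| Excluded if more than 10% missed (below 90% attended) | 0.90 x 48 = 43.2 | 0.90 x 72 = 64.8 |

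The first reading removes only runners who barely trained. The second removes anyone who misses 5 or more runs (or 8 or more sessions).

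**3. Whether compliance may differ by arm.** From the totals in Tables 8 and 10, over the four week types:

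- TRIMPs, THR / POL: 384/324 = 480/405 = 576/486 = 288/243 = 1.185, so THR is 18.5% higher.
- Zone 3 minutes, POL / THR: 36/24 = 45/30 = 54/36 = 27/18 = 1.50, so POL is 50% higher.
- Weekly minutes and session counts are equal.

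The programmes differ in what they demand, but the two measures point in opposite directions. Which arm would lose more runners cannot be read from the protocol.

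**4. Precision.** Inputs from Sample Size Calculation: SD 60 s, difference 60 s, alpha 0.05 (two-sided assumed, since sidedness is not stated), power 80%. The plan's 8 per group is not reproduced for independent samples: 2 x (1.960 + 0.842)^2 x (60/60)^2 = 15.7, so 16 per group (13 if one-sided). The value 8 comes from the one-sample or paired formula, (1.960 + 0.842)^2 = 7.85. That is a separate matter, but it means removals come from a trial already short of power.

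Power of the two-sided t test uses the noncentral t distribution with df = n1 + n2 - 2 and noncentrality (60/60) / sqrt(1/n1 + 1/n2):

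| Runners analysed | Power |
|---|---|
| 10 v 10 | 56% |
| 9 v 10 | 54% |
| 8 v 8 | 46% |
| 9 v 7 | 46% |
| 7 v 7 | 41% |

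**5. Possible bias, illustration only.** None of these inputs is in the protocol: SD of change 60 s (the protocol does not say that its 60 s is an SD of change), correlation rho between adherence and improvement 0.3 to 0.5, no true effect, the least adherent 30% removed from one arm and 0% or 10% from the other. If the two are jointly normal, removing the lowest fraction p shifts an arm's mean improvement by rho x SD x phi(z_p)/(1 - p). The last factor is 0.348/0.7 = 0.497 at p = 0.3 and 0.175/0.9 = 0.195 at p = 0.1.

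- 30% v 10%: 60 x (0.497 - 0.195) x rho = 5.4 s (rho 0.3) to 9.1 s (rho 0.5).
- 30% v 0%: 60 x 0.497 x rho = 8.9 s (rho 0.3) to 14.9 s (rho 0.5).

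The range is about 5 to 15 s, or 9% to 25% of the 60 s target.

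**The case against.** **Removal from the analysis is not stated.** Table 4 does not say that runners who meet the line lose their final test or leave the analysis, and a statistical analysis plan that is not shown may define the analysis set. This stands, and it makes the bias conditional. It does not rescue the line: an analysis set of all randomised runners would conflict with an exclusion that Table 4 states.

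**The wording may be a slip.** The English is visibly translated, and a symbol or a prefix may have been lost in translation or extraction. This stands, so the literal 10% should not be held against the plan as a deliberate choice. A restored symbol would settle the direction but not the timing.

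**On one reading little happens.** If attendance below 10% was meant, those removed are in effect dropouts, and extra removals could be close to none. This also stands. The 30% removal in the illustration fits only the strict reading. Even then, 5 to 15 s is less than the standard error of the difference at 10 v 10, 60 x sqrt(2/10) = 27 s.

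**Stronger readings to avoid.** A reader might infer that the comparison is already biased, that the unclear threshold is a second source of bias, or that THR is flattered because its load is higher. The protocol gives no compliance data. An unclear threshold leaves room for discretion but does not bias anything by itself. And THR's higher TRIMPs are set against POL's greater Zone 3 time.

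**Conclusion.** The point holds in conditional form. Table 4 places a post-randomisation behaviour among the exclusions, with a threshold that could lie anywhere from about 5 to about 43 of 48 runs, to be applied in an open trial. If runners are dropped under it, the comparison can be biased when removals differ between arms in number or prognosis and adherence is related to outcome. The direction is unknown.

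The size depends on the reading: few removals under a 10% attendance cut-off, possibly many under a 90% one. Each costs 10% of an arm; going from 10 v 10 to 9 v 7 lowers power by about 10 percentage points on the plan's SD and difference. The 5 to 15 s figure rests wholly on assumed removal rates, correlation and SD of change, and shows scale rather than an estimate. The correction should come before the final assessments, because a test not done on an excluded runner cannot be recovered later.

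**What to change.** - Delete the compliance line from Table 4.
- State that all randomised runners are invited to the final 5 km test already scheduled, whatever their attendance, subject to consent and the trial's own safety provisions, and that the primary analysis keeps each runner in the arm assigned.
- Report sessions completed by arm.
- If a compliance threshold is wanted, state its direction, its denominator (runs only, or runs plus strength sessions) and its period, and use it only for a supplementary per-protocol analysis.

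The cost is a change of wording and the effort of bringing low adherers back for a planned test. Keeping them may dilute the estimated difference slightly.
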